The PHQ-9 is a nine-item instrument that measures depression-related symptoms and functional impairment. Each item is scored on a four-point Likert scale and values range from 0 ("Not bothered at all") to 3 ("Bothered nearly every day.") The items' values are summed to determine the instrument's score. PHQ-9 values of 10 and 15 represent moderate and moderately severe depression respectively.

Sleeplessness - PROMIS short form 4a

This eight item instrument measures sleep disturbance and sleep-related impairment.

8.2 Secondary Endpoints: Secondary endpoints consisted of the following:

Effectiveness: There are two secondary effectiveness endpoints:

1. In the Nu-V3 device treatment arm, the study will report the mean time from treatment initiation to reduction of symptoms of at least 30% in any of the four domains of symptom measurement.
2. In both the Nu-V3 device treatment arm and the observation arm, the study will report the mean percentage change in symptoms severity from initiation to 12 and 24 weeks for each instrument.

Additional secondary endpoints of this study are:

- Mean improvement in quality of life measured with Patient's Global Impression of Change (PGIC) between the treatment and usual care arm, and

- Mean improvement in activities of daily living via Perceived Treatment Benefit Form (PTB-6) between the treatment and usual care arm.

8.3 Sub-Analyses: Sub-Analyses consist of the following:

The study has several sub-analyses. They include:

- The mean number of weeks that chronic pain, anxiety, depression, and sleeplessness response are achieved and sustained, without utilization of another device or change in other treatments, during the full 24-week intervention in the Nu-V3 device treatment arm.
- The mean number of weeks to initial benefit from Nu-V3 device use in the Nu-V3 device treatment arm. Benefit is defined as a reduction of at least 30% of symptoms in at least one of chronic pain, anxiety, depression, or sleeplessness.
- **The device's comfort-of-use, and patient's perceived treatment benefit** in the Nu-V3 device treatment arm.

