Date (dd/mmm/yyyy): ____/____/____

In the past 7 days...

		Very poor	Poor	Fair	Good	Very good
1	My sleep quality was					

In the past 7 days...

		Not at all	A little bit	Somewhat	Quite a bit	Very much
2	My sleep was refreshing.					
3	I had a problem with my sleep.....					
4	I had difficulty falling asleep					

PATIENTS' GLOBAL IMPRESSION OF CHANGE (PGIC) SCALE

Subject ID: _____

Date (dd/mmm/yyyy): ____/____/____

Chief Complaint (Presenting Problem): _____

Since beginning treatment at this clinic, how would you describe the change (if any) in ACTIVITY LIMITATIONS, SYMPTOMS, EMOTIONS, and OVERALL QUALITY OF LIFE, related to your painful condition? Please circle the number below, that matches your degree of change since beginning care at this clinic for the above stated chief complaint.

No change	Almost the same	A little better	Somewhat better	Moderately better	Better	A great deal better
1	2	3	4	5	6	7

Explanation:

- | | |
|--|--|
| 
 1 = No change (or condition has got worse) 2 = Almost the same, hardly any change at all 3 = A little better, but no noticeable change 4 = Somewhat better, but the change has not made any real difference | 
 5 = Moderately better, and a slight but noticeable change 6 = Better, and a definite improvement that has made a real and worthwhile difference 7 = A great deal better, and a considerable improvement that has made all the difference |
|--|--|

Patient's signature: _____

NOTE TO HEALTH CARE PROVIDER

A significant, favorable change is a score of 5-7.
 No significant change is a 1-4 response.
 Note, this a dichotomous scale (5-7 = yes; 1-4 = no).
 A 2-point change is significant from their last reported score.

[figure not shown]
Reference: Hurst H, Bolton J. Assessing the clinical significance of change scores recorded on subjective outcome measures. Journal of Manipulative Physiological Therapeutics (JMPT) 2004;27:26-35.

Subject ID _____ Date (DD/MMM/YYYY): ____/____/____

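### The PGIC secondary endpoint dates change from the start of clinic care, not from randomisation, and its quality-of-life label claims more than one pooled item can show

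*Protocol*

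**What the plan says.** Protocol 8.2 (Secondary Endpoints) gives two additional secondary endpoints. One is "Mean improvement in quality of life measured with Patient's Global Impression of Change (PGIC) between the treatment and usual care arm".

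The PGIC form is printed in Appendix 8. Its stem reads "Since beginning treatment at this clinic, how would you describe the change (if any) in ACTIVITY LIMITATIONS, SYMPTOMS, EMOTIONS, and OVERALL QUALITY OF LIFE", and the same sentence then limits the question to the participant's painful condition. The next sentence asks for the number that "matches your degree of change since beginning care at this clinic for the above stated chief complaint". The answer is one rating from 1 to 7.

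The tables in 4.1 schedule the PGIC weekly from week 2 in the device arm and at weeks 4, 8 and 12 in the control arm. It is not scheduled at week 1 in either arm. Section 4.0 has participants in both arms continue existing treatment unless a change is discussed with the investigator, and it offers controls the device after 12 weeks.

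**The concern.** A between-arm comparison of perceived change needs one starting point shared by both arms, and in a randomised trial that point is randomisation or baseline. The form gives a different one: the start of treatment, or of care, at the clinic. Allocation itself decides whether a participant has an obvious new treatment start, and in an open-label trial every participant knows the allocation. The same words can therefore point to different dates in the two arms.

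The second issue is what the number means. Section 8.2 would report it as quality of life, but the item asks for one judgement on several things at once. A participant whose symptoms alone improved could score high, and the result would be reported as a quality-of-life gain.

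The stake is how one secondary result is interpreted. No primary endpoint uses this form. However, the wording is fixed in the protocol's own appendix, and no later analysis can recover a reference point that participants were never given.

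**Working it through.** The plan states no figure for this endpoint, so there is nothing to reproduce. The check compares the endpoint, the form and the schedule.

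**1. The anchor.** Section 8.2 needs change over the randomised comparison. The form dates change first from treatment and then from care ("your degree of change since beginning care at this clinic"). These are two different phrases, and neither refers to enrolment, baseline or randomisation.

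**2. What starts at week 1.**

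| | Device arm | Control arm |
|---|---|---|
| New at week 1 (4.1) | Device placed, then weekly office assessments | No device in weeks 1 to 12 |
| Background care (4.0) | Continues | Continues |
| PGIC (4.1) | Weekly from week 2 | Weeks 4, 8, 12 |

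Both arms answer the same form, but only one has a new treatment from which to date change.

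**3. The possible readings.**
- Both arms date from enrolment. The comparison is sound, but the form does not tell participants to do this.
- Both arms date from earlier clinic care. Change before randomisation enters both arms. Randomisation balances it on average, but it obscures the change the trial is about.
- Device participants date from the device, and controls from earlier care or from nothing in particular. The comparison is biased. If controls credit earlier care, their mean rises and the difference shrinks. If they feel that nothing has begun, their ratings fall and the difference grows.

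**4. How far the recall periods could differ (illustration).**
- Comparative period: 12 weeks × 7 = 84 days (4.0).
- Medication for the four symptoms must be unchanged for 60 days before entry (3.2).
- Assumption: a control dates from current medication, that medication was started at this clinic, and a start counts as a change. Recall at week 12 is then at least 60 + 84 = 144 days, or 144 / 7 = 20.6 weeks.
- A device participant dating from the device recalls 84 days. The gap is at least 144 − 84 = 60 days.
- If both date from enrolment, the gap is 84 − 84 = 0 days.

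The gap can thus be 0, or 60 days or more under the stated assumption. It is a length of recall, not a number of scale points, and the protocol does not say which case applies.

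**5. The content.** The rating covers "ACTIVITY LIMITATIONS, SYMPTOMS, EMOTIONS, and OVERALL QUALITY OF LIFE, related to your painful condition". That is four elements in one number, so a change in one cannot be told from a change in another. Section 3.1 admits participants whose primary symptom is anxiety, depression or sleeplessness, and for them the painful-condition wording may not apply. The form also disagrees with itself here, since its next sentence refers to the chief complaint. The instruments listed in the 4.1 footnotes and printed in Appendix 8 include no separate quality-of-life questionnaire, although 4.0 says quality of life is asked about at baseline and at later visits.

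**The case against.** The strongest reply is that both arms receive one form and are randomised 1:1, so earlier attendance at the clinic should balance on average. Section 4.0 also describes control care as treatment dated from enrolment, and the control PGIC is first taken after week 1, which fits change since study start. Nothing in the protocol says that sites were already treating their participants for the complaint.

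Much of this stands, and it rules out several stronger readings that a reader might infer:
- That the arms are in fact compared over different periods. This is a risk of the wording. The protocol does not establish it, and the gap may be 0.
- That a control new to the site has no anchor. For that person, care at the clinic can begin with the study's baseline visit.
- That quality of life is not measured at all. It is one of the four elements named in the stem; it is just not measured separately.
- That a bias in scale points can be quoted. That would need the share of controls who look back to earlier care and the points they add for it. The protocol gives neither, and a shift applied to controls alone would leave out the same effect in the device arm.

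The objection does not remove the core. Randomisation balances care history, but it does not balance how a phrase is understood when allocation determines whether a new treatment has begun. Even the favourable reading depends on participants supplying an anchor that the form does not state.

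**Conclusion.** The point holds in a limited form. The anchor of this between-arm endpoint is not randomisation. It may be read differently by arm, or may bring earlier change into both arms. The size and direction of any resulting bias are unknown, and zero is possible. Separately, and without any assumption about how participants read the anchor, the label in 8.2 overstates what a single pooled, pain-tied rating can show about quality of life.

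The severity is minor, because this is an additional secondary endpoint in a Phase II trial and the primary effectiveness endpoint rests on other instruments. The concern about the anchor rests on the form being used as printed in Appendix 8.

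**What to change.** In the ePRO version of the PGIC, identically for both arms:
- replace both clinic phrases with 'since you joined this study';
- replace the reference to a painful condition with the participant's stated chief complaint, which the form already records.

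In 8.2, name the endpoint 'patient global impression of change' and drop the quality-of-life label.

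The cost is a few words in the ePRO and one endpoint name. The downside is a slight departure from the printed stem. The form cites a published source, and the protocol does not show whether its stem may be altered. Ratings already given under the present wording cannot be re-anchored. Relabelling also leaves the quality-of-life questionnaires mentioned in 4.0 without an endpoint, so that text should be reconciled with the instruments actually listed.

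### The PGIC question gives participants without pain two conflicting things to rate, so the between-arm PGIC secondary endpoint carries avoidable measurement error and possible dilution

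*Protocol*

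**What the plan says.** Section 8.2 of the Protocol lists as an additional secondary endpoint "Mean improvement in quality of life measured with Patient's Global Impression of Change (PGIC) between the treatment and usual care arm". It is the only instrument that section names for quality of life.

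The form itself is in Appendix 8. It opens with a free-text field for the chief complaint. The question then asks about change in activity limitations, symptoms, emotions and "OVERALL QUALITY OF LIFE, related to your painful condition". The sentence that follows tells the participant to circle the number "that matches your degree of change since beginning care at this clinic for the above stated chief complaint".

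Answers run from 1 to 7. Score 1 covers both no change and worsening. Below the scale, under "NOTE TO HEALTH CARE PROVIDER", the form says "Note, this a dichotomous scale (5-7 = yes; 1-4 = no" and then "A 2-point change is significant from their last reported score".

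Under section 3.1 any one of the four symptoms is enough for entry, and Appendix 9 has the participant choose a single primary symptom. The tables in section 4.1 schedule the patient PGIC in both arms (weeks 4, 8 and 12 for controls, weekly from week 2 for the device arm). Only one version of the form is shown.

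**The concern.** A participant who enters for anxiety and has no pain meets two instructions in one item. The first asks about a painful condition that this person does not have. The second asks about the complaint entered at the top of the form. The Protocol does not say which governs.

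If some participants follow the first and some the second, the score does not mean the same thing for everyone. A person without pain who takes the stem literally has nothing to report and will probably circle the bottom of the scale, whatever has happened to the anxiety. Someone enrolled for depression who also has pain may rate the pain instead. The first pattern pulls the arm difference toward zero, and the second adds error. An analysis plan cannot repair this afterwards, because the answers do not record which question was being answered.

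**Working it through.** The Protocol states no PGIC effect size, standard deviation, responder rate, power or number of participants without pain, so there is no figure to reproduce. The check sets the texts side by side and then bounds the consequence.

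**Step 1: the two instructions.**

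| Element of the form | What it points the participant to |
|---|---|
| Chief-complaint field | Any presenting problem, free text |
| Question stem | "related to your painful condition" |
| Answer instruction | The chief complaint entered above |

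For a participant whose chief complaint is pain, the rows agree. For one without pain, the second row conflicts with the other two. Section 3.1 allows such participants.

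**Step 2: size of any dilution.** Let p be the share of participants without pain, q the share of those who answer literally about pain, and Δ the true arm difference in mean score. Assume that Δ is the same with and without pain, that p and q are equal in the two arms, and that literal readers without pain score alike in both arms. Then

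observed difference = (1 − p)Δ + p(1 − q)Δ + pq × 0 = Δ(1 − pq),

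so the proportional loss is pq. Neither p nor q is in the Protocol. Over assumed ranges:

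| p (assumed) | q = 0% | q = 50% | q = 100% |
|---|---|---|---|
| 25% | 0% | 12.5% | 25% |
| 50% | 0% | 25% | 50% |
| 75% | 0% | 37.5% | 75% |

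The loss is zero if everyone follows the chief-complaint sentence. It can never exceed p.

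To put this in scale points, take a normal latent score with SD 1.8, control mean 3 and shift 1.0, cut into scores 1 to 7 (all assumed). The mean scores are 3.11 and 4.00, a difference of 0.89. A loss of 12.5% leaves 0.89 × 0.875 = 0.78, and a loss of 37.5% leaves 0.89 × 0.625 = 0.56.

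**Step 3: is the mean itself a fault?** The mean and the 5-7 proportion can disagree. If every control scores 1 and every device participant scores 4, the means differ by 4 − 1 = 3 with 0% responders in each arm. If one arm scores all 4 and the other half 1 and half 7, both means are 4.0 but the responder shares are 0% and 50%. These are artificial extremes and show only that the two summaries answer different questions.

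Under the same latent model (SD 1.8, two-sided alpha 0.05, control means 2 to 4, no dropout), power at the two ends of the planned total of 100-200 is:

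| Latent shift | Total N | Mean score | Proportion 5-7 |
|---|---|---|---|
| 0.5 | 100 | 25-27% | 13-19% |
| 0.5 | 200 | 45-48% | 21-34% |
| 1.0 | 100 | 75-77% | 40-59% |
| 1.0 | 200 | 96-97% | 68-88% |

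In these scenarios the mean is the more powerful summary. The split also hides worsening further, because it pools scores 1 to 4, whereas on the full scale only score 1 mixes worsening with no change.

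**The case against.** The strongest reply is that the form already contains its own answer. The sentence after the pain wording ties the rating to the chief complaint, the field for that complaint is open, and the stem lists symptoms, emotions and quality of life. A participant with anxiety can write anxiety and rate it. This stands. A reader who stops at the stem might infer that people without pain can only report no change, or that the PGIC does not measure their change at all. The form does not support that: its wording is inconsistent for them, but it does not shut them out.

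A reader might also infer a loss of 25-75%. That needs every participant without pain to read the stem literally, and it needs a pain-free share that the Protocol does not give. The 75% end further assumes four equal cohorts with no overlap. Section 1.1 says these symptoms often cluster, and section 3.1 provides for a qualifying second symptom, so a non-pain primary symptom does not imply absence of pain.

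Finally, a reader might take the dichotomy on the form to mean that section 8.2 uses the wrong summary. The note is addressed to the provider and concerns how to read one patient's score. The line after it uses the points of the scale. A mean of a 7-point score is a legitimate between-arm summary, and a responder analysis may be in a statistical analysis plan that is not shown.

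None of this removes the inconsistency in the question itself. It limits what may be claimed about its effect.

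**Conclusion.** The point holds as a defect in question wording. The PGIC item gives participants without pain two conflicting referents, and section 3.1 makes such participants eligible. The consequence is measurement error and possible dilution in one between-arm secondary endpoint.

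The size cannot be derived from the Protocol. Under the assumptions of the check, it runs from zero up to the full share of participants without pain, and where it falls depends on how many of them read the stem literally.

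The choice of the mean in section 8.2 is not an error. The primary effectiveness analysis rests on other instruments and is unaffected, so this is a minor point, worth correcting because it is cheap before collection and cannot be undone after.

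**What to change.** Before data are collected, replace the reference to a painful condition in the ePRO stem with the chief complaint, and pre-fill that field with the primary symptom under which the participant was enrolled. The stem, the field and the answer instruction then all point to the same thing in both arms.

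Keep the mean as the section 8.2 summary. The proportion scoring 5-7 at week 12 may be reported by arm as support, since the provider note treats 1-4 as no significant change. Week 12 is scheduled in both arms and comes before controls are offered the crossover.

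The cost is one phrase and one pre-filled field on the ePRO, plus, if wanted, one sentence in section 8.2. The downside is a change to the wording of a published form. Whether its terms allow that cannot be judged from the Protocol and should be confirmed first.

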Subjects randomized to the observation control arm of the study will undergo the following regimen:

- At the baseline visit, patients will be asked to complete study questionnaires (Appendix 11) regarding all the following symptoms: chronic pain, anxiety, depression, and/or sleeplessness, as well as their quality of life, active medications, medical history, and demographical information. The subject's primary symptom of concern will also be notated at baseline.
- At each subsequent visit, patients will be asked to complete study questionnaires regarding all the following symptoms: chronic pain, anxiety, depression, and/or sleeplessness, as well as their activity level and quality of life.
- Patients should not change their existing forms of treatment or medications without discussion with the study investigator.
- At completion of 12 weeks of standard of care treatment post study enrollment, observation (control arm) subjects will be offered a crossover into the treatment arm of the study for an additional 24 weeks.

Sample size

For this Phase II study, a total of 100-200 subjects will be randomized 1:1 to either the Nu-V3 treatment arm or to the observation treatment arm (SOC, control).

Recruitment

Participants are enrolled into relevant symptom cohorts based on their chronic pain, anxiety, depression, and/or sleeplessness symptom presentation at baseline and treated with the Nu-V3 device for 24 weeks.

Analyses

Interim analysis of reported data will be based on baseline symptom cohort and conducted at 6, 12, 18, and 24 weeks during this time. The participant will be evaluated after the initial 12-week treatment period to assess for further therapeutic need. Upon having three consecutive weeks of mean symptom reduction of $\geq 70\%$ via patient reported numerical scales, the participant will continue as described in the study assessments table, but without device therapy. Then if the participant's primary

symptom score increases at any time by $\geq 20\%$, they may again continue device therapy until week 24, as depicted in section 4.1.

Study subjects randomized to the observation arm will be offered the opportunity to cross-over to the Nu-V3 study treatment arm upon completion of the initial 12-week observation study period.

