4.1 Phase II Study Assessment Tables

 Initial Study Assessments Table 												
*Evaluations are completed weekly, every 7 days ± 3 days												
Nu-V3 Treatment Arm Evaluation*	Week 1	Week 2	Week 3	Week 4	Week 5	Week 6	Week 7	Week 8	Week 9	Week 10	Week 11	Week 12
Informed Consent	x											
Inclusion and Exclusion ¹	x											
Patient Registration ¹	x											
Medications Form ¹	x			x				x				x
Patient Onboarding and Orientation ²	x											
In office assessment	x	x	x	x	x	x	x	x	x	x	x	x
New Device Placed ³	x				x				x			
Pad Replaced ³		x	x	x		x	x	x		x	x	x
Treatment Forms ¹	x	x	x	x	x	x	x	x	x	x	x	x
No Device												
HRV Assessment (optional) ⁴	x	x	x	x	x	x	x	x	x	x	x	x
ePRO Questionnaires ⁵	x	x	x	x	x	x	x	x	x	x	x	x
Patients' Global Impression of Change ePRO form (PGIC) ⁵		x	x	x	x	x	x	x	x	x	x	x
Providers' Global Impression of Change ePRO form (PGIC) ¹		x		x		x		x		x		x
Optional Patient Media Testimony ⁶	x	x		x				x				x

1. Inclusion/Exclusion, Registration, Medications, Treatment, and Providers' PGIC forms to be completed by site via online module.
2. Patient Onboarding and Orientation includes introductory demographics form, Nu-V3 patient training video
3. Upon having three consecutive weeks of primary symptom reduction of $\geq 70\%$ via patient reported numerical scales from baseline, the participant will have reached symptom response plateau and will continue as described in the study assessments table, but without device therapy. Then if the participant's primary symptom score increases at any time by $\geq 20\%$ from the symptom response plateau, they may again continue device therapy until week 24.
4. (Optional) HRV assessment will be conducted before the first treatment and again 15-20 minutes following the first treatment. The HRV assessment will also be conducted prior to each weekly treatment. This assessment is applicable to participating sites per the clinical trial agreement. Contact the clinical trial manager for Information.
5. ePRO questionnaires completed on patient's mobile device: DQ-9 (baseline), PTB-7, PEG, GAD-7, PHQ-9, PROMIS 4a, PGIC
6. If patient consents to media testimony, site will collect via study collection process.

Nu-Life Solutions Miniaturized Wearable Medical Technology - NuJ ³	Study Assessments Table											NuJ ³
	*Evaluations are completed weekly, every 7 days ±3 days											

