Nu-V3 Treatment Arm Evaluation*	Week 13	Week 14	Week 15	Week 16	Week 17	Week 18	Week 19	Week 20	Week 21	Week 22	Week 23	Week 24
Medications Form ¹				x				x				x
In office assessment	x	x		x	x		x	x		x	x	x
New Device Placed ²	x			x			x			x		
Pad Replaced ²		x			x			x			x	
Treatment Forms ¹	x	x		x	x		x	x		x	x	
No Device			x			x			x			x
HRV Assessment (optional) ³	x	x		x	x		x	x		x	x	
ePRO Questionnaires ⁴	x	x	x	x	x	x	x	x	x	x	x	x
Patients' Global Impression of Change ePRO form (PGIC) ⁴	x	x	x	x	x	x	x	x	x	x	x	x
Providers' Global Impression of Change ePRO form (PGIC) ¹		x			x			x		x	x	
Optional Patient Media Testimony ⁵	x	x		x				x				x

1. Providers' PGIC form, Medications and Treatment forms to be completed by site via online module.
2. Upon having three consecutive weeks of mean symptom reduction of ≥70% via patient reported numerical scales, the participant will continue as described in the study assessments table, but without device therapy. Then if the participant's primary symptom score increases at any time by ≥20%, they may again continue device therapy until week 24.
3. (Optional) HRV assessment before the first treatment and again 15-20 minutes following the first treatment. HRV assessment will also be conducted prior to each weekly treatment. This assessment is applicable to participating sites per the clinical trial agreement. Contact the clinical trial manager for information.
4. ePRO questionnaires completed on patient's mobile device: DQ-9 (baseline), PTB-7, PEG, GAD-7, PHQ-9, PROMIS 4a, PGIC
5. If patient consents to media testimony, site will collect via study collection process.

Nu-Life Solutions Miniaturized Wearable Medical Technology - NuJ ³	Control Study Assessments Table											NuJ ³
	*Evaluations are completed weekly, every 7 days ±3 days											
Control Arm Evaluation*	Week 1	Week 2	Week 3	Week 4	Week 5	Week 6	Week 7	Week 8	Week 9	Week 10	Week 11	Week 12
Informed Consent	x											
Inclusion and Exclusion ¹	x											
Patient Registration ¹	x											
Medications Form ¹	x			x				x				x
Patient Onboarding and Orientation ²	x											
In office assessment	x			x				x				x
No Device	x	x	x	x	x	x	x	x	x	x	x	x
ePRO Questionnaires ³	x			x				x				x
Patients' Global Impression of Change ePRO form (PGIC) ³				x				x				x

1. Inclusion/Exclusion, Registration, Medications, Treatment, and Providers' PGIC forms to be completed by site via online module.

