[figure not shown]

Form PTB-6: Patient's Perceived Treatment Benefit

1. On a scale of 0-10, how much benefit do you feel you have received from the Nu-V3 treatment in helping your symptoms?

[figure not shown]
2. On a scale of 0-10, how much has your daily activity level improved?

3. Do you feel that your as needed medications have decreased from using the device?

Yes
 No

4. How comfortable was the Nu-V3 Device to wear?

5. Have you had any major discomfort from the device?

Yes; please continue to question 6
 No

6. If yes to question 5, did adjusting the device correct the discomfort?

Yes
 No

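### The only daily-activity item on the PTB-6 names no starting point and is scheduled at different intervals in the two arms, so the arms may report improvement over different periods

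*Protocol*

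**What the plan says.** Protocol section 8.2 lists, among the additional secondary endpoints, "Mean improvement in activities of daily living via Perceived Treatment Benefit Form (PTB-6) between the treatment and usual care arm". In Appendix 8, the PTB-6 has six items. Only item 2 concerns daily activity: "On a scale of 0-10, how much has your daily activity level improved". Item 1, just before it, asks about benefit received from the Nu-V3 treatment.

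The schedule is in section 4.1. The footnote on the packet is the same for both arms: "ePRO questionnaires completed on patient's mobile device: DQ-9 (baseline), PTB-7, PEG, GAD-7, PHQ-9, PROMIS 4a, PGIC". For weeks 1 to 12, the device-arm row ("ePRO Questionnaires ⁵") is marked every week. The control-arm row ("ePRO Questionnaires ³") is marked at weeks 1, 4, 8 and 12 only, yet the header of that table says "Evaluations are completed weekly, every 7 days ±3 days".

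Section 4.0 describes the questionnaires for each arm. Activity level is absent from the baseline list in both arms and appears only for subsequent visits ("as well as their activity level and quality of life").

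**The concern.** Item 2 asks for a change, and a change needs a starting point. The respondent is given none and has to choose one: the last time the form was completed, the start of the study, or the day the device was first worn. If the choice, or the interval it implies, differs by arm, the between-arm mean compares improvement over different lengths of time. Two arms with the same true course could then differ, or a real difference could be hidden.

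At stake is one secondary endpoint. The four primary symptom instruments are not affected, because each states its own recall period. An analysis plan can choose the visit and the model, but it cannot supply a reference period that patients were never shown. The weakness therefore lies in the protocol and its form.

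**Working it through.** No figure in the protocol bears on this point, so the check sets the texts side by side and counts schedule marks.

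**Reference period by form (Appendix 8)**

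- PEG: past week.
- GAD-7 and PHQ-9: last 2 weeks.
- PROMIS sleep form: past 7 days.
- PGIC, which like item 2 asks about change: since the start of treatment at the clinic.
- PTB-6 item 2: none in the printed text.

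**Administrations in weeks 1 to 12 (section 4.1)**

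The device arm has 12 and the control arm has 4. This assumes that the PTB-7 in the footnotes is the PTB-6 of section 8.2 and Appendix 8.

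**Look-back in nominal weeks at the shared visits after Week 1**

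| Visit | Since last form, device | Since last form, control | Since Week 1, either arm |
|---|---|---|---|
| Week 4 | 4 − 3 = 1 | 4 − 1 = 3 | 4 − 1 = 3 |
| Week 8 | 8 − 7 = 1 | 8 − 4 = 4 | 8 − 1 = 7 |
| Week 12 | 12 − 11 = 1 | 12 − 8 = 4 | 12 − 1 = 11 |

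The first device is placed at Week 1, so for the device arm a reading of 'since the device' is the same as 'since Week 1'.

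**Possible pairs at Week 12 (device : control)**

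- Both answer since the last form: 1 : 4.
- Both answer since Week 1: 11 : 11.
- Device since the last form, control since Week 1: 1 : 11.
- Device since Week 1 (the reading item 1 may cue), control since the last form: 11 : 4.

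In the first and third pairs the device arm has the shorter look-back. In the fourth it has the longer one. Nothing in the protocol says how common each reading is, so the direction cannot be fixed.

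**If the control table's header is right and its marks are wrong**

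The time since the last form would then be 1 week in both arms, and the schedule part of the problem would disappear. The missing starting point and the one-sided cue from item 1 would remain.

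**Week 1**

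The packet is marked at Week 1 in both arms, and the footnote limits only the demographics form to baseline. The PGIC has its own row, which starts at Week 2 in the device arm and Week 4 in the control arm. The PTB form has no such exemption, although section 4.0 places activity level only at later visits.

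**The case against.** Several points on the other side have weight.

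- **The PGIC may act as a cue.** It precedes the PTB-6 in Appendix 8, states a starting point and covers activity limitations, so some patients may carry its reference point over. This could soften the problem. However, the order in Appendix 8 is not the order in the schedule footnotes, and a carried-over cue does not replace a stated period.
- **PTB-6 and PTB-7 may not be the same form.** A PTB-7 could be worded differently. The statement about frequency depends on treating them as one form, and the conflict of names is itself something to correct.
- **Figures are missing from the text at hand,** one before the form's title and one after item 1. A time frame inside them cannot be excluded. The printed question has none.
- **The Week 1 mark covers the whole packet,** and section 4.0 suggests that activity level was not meant to be asked then. That makes it a contradiction to reconcile, not proof that the item is used at Week 1. The protocol nowhere specifies an analysis of change from the Week 1 answer.

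A reader might go further and infer a bias of a definite size or sign. The documents do not support that. They give no rate of improvement and no share of patients using each reading, and the pairs above point both ways.

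A reader might also extend the point to the comfort and discomfort items, such as "Have you had any major discomfort from the device", and infer that weeks without the device dilute the results. Those items also state no period. However, section 8.3 reports comfort in the device arm only, so they have no bearing on a comparison between arms. Their past-tense wording does not confine the answer to the current week, and restricting a summary to weeks of wear is ordinary analysis-plan work.

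**Conclusion.** The point holds as a weakness in one secondary endpoint. The single item behind the daily-activity comparison states no starting point in its printed text. As the tables are marked, the arms complete it at different intervals, and the item before it may suggest a starting point to device users only. The arms may therefore report improvement over different periods. At Week 12 the nominal look-back could be 1 week against 4, or 11 weeks against 4, depending on how patients read the question. The resulting bias is possible but not demonstrated, and its size and direction are unknown.

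This rests on three assumptions: that PTB-6 and PTB-7 are one form, that the marks in the control table stand over its header, and that the figures not shown contain no time frame. It concerns weeks 1 to 12, after which controls may cross over to the device.

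**What to change.** - Add one reference point to item 2, worded identically in both arms, for example by opening the question with 'Since you enrolled in this study'. This keeps the item a measure of perceived improvement. Replacing it with a rating of current activity would change what is measured and is not needed.
- Do not ask the item at Week 1, and say so in the schedule footnotes, so that section 4.1 agrees with section 4.0.
- Compare the arms at the visits common to both: weeks 4, 8 and 12.
- Use one name for the form throughout, and reconcile the control table's header with its marks.

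The cost is a short change to one ePRO item and edits to the schedule tables. The one drawback is that answers already collected under the present wording would not be directly comparable with later ones.
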